#### 10. SAFETY AND TOLERABILITY ANALYSIS

The safety analysis will be run on the Safety population. The analysis of safety assessments in this study will include summaries or data listings of the following safety and tolerability data collected for each subject:

- Adverse Events including Serious Adverse Events
- Clinical Laboratory Investigations including coagulation studies
- Concomitant Medications
- Vital Signs
- Physical exam including height and weight
- Investigator visual skin assessments
- Electrocardiogram Parameters
- Pregnancy Tests

Protocol: CP-2019-001 Page 21 of 26

Final Version 1.0

#### 10.1 Adverse Events

All AEs, treatment-emergent adverse events (TEAEs), and SAEs will be coded using MedDRA, version 22.0.

Adverse events are categorized as either pre-treatment adverse events or treatmentemergent adverse events based on the response to the CRF question "Did the AE occur prior to patch administration?"

An AE summary table or listing will be presented for the following:

- TEAEs by severity
- TEAEs leading to study drug discontinuation
- TEAEs by relationship
- SAEs

Summaries of incidence rates (frequencies and percentages) of individual TEAEs by MedDRA SOC and preferred term will be prepared if there are a sufficient number of adverse events.

Each subject will be counted only once within each summation level (SOC; preferred term).

In the AE data listings, all AEs will be displayed. AEs that are treatment-emergent will be flagged.

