6.1.2 Visit 2, Day 1 Randomization

- Perform physical exam, including weight
- Perform investigator skin assessment of the upper arm where patches are intended to be applied
- Record vital signs: temperature, respiratory rate (RR), blood pressure (BP), and heart rate (HR)
- Record concomitant medications, including medication taken to treat cluster headaches
- Urine pregnancy for all WOCBP
- Record Adverse events
- Train the subject on how to apply the patches to the upper arm with the demo applicator and have the subject practice applying the demo patches to his/her arm 2-3 times (more is allowable, if necessary)
- Review the definition of a qualifying cluster headache for the study with the subjects
- Record that the subject can apply patches with the applicator unaided
- Reconfirm subject's eligibility based on inclusion/exclusion criteria
- Randomize subject
- Dispense CTM kit that includes the applicator and one dose (each dose consists of 2 patches) as assigned by the RTSM in Medidata

- Provide instructions for scheduling the next visit within 1-8 days of experiencing and treating a qualifying cluster headache with C213
- Remind the subject that if rescue therapy is required, rescue therapy other than a triptan or ergot is permitted at or after 20 minutes post study drug administration.
- Provide eDiary training necessary and dispense the eDiary

6.1.3 Double-Blind Treatment Phase: Day 1 through up to 48 Weeks [336 Days + or – 7 days]

Subjects will have up to 48 weeks to confirm and treat a qualifying cluster headache. Subjects will be instructed to complete the eDiary at the time of a suspected cluster headache. Once the eDiary confirms that the subject has a "qualifying" cluster headache, the subject will follow the steps provided to self-administer the study drug.

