6.2.11 Assessment of Adverse Events

AEs are collected from the time of signing the informed consent form and throughout the study duration. New systemic and skin AEs will be recorded on the appropriate source document and eCRF.

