8.2 Adverse Event Definitions

8.2.1 Adverse Events (Adverse Experiences)

An AE is any untoward medical event that occurs in a clinical investigation, where a subject is administered a medicinal (investigational) product or medical device, and which does not necessarily have a causal relationship between the event and the treatment. An AE can be any unfavorable and unintended sign or symptom, including clinically significant abnormal laboratory result, concomitant illness, or worsening of an existing medical condition.

A Treatment Emergent Adverse Event (TEAE) is an event that emerges during treatment having been absent pre-treatment or worsens relative to the pre-treatment state.

Collection of systemic and skin AEs will be initiated after the ICF has been signed and conclude when the post-study procedures are completed (or Early Discontinuation). This includes the time between screening and the first dosing.

Abnormal laboratory tests that are clinically significant, as determined by the investigator, should be reported as AEs if:

- the test result is associated with accompanying symptoms;
- the test result requires additional diagnostic testing or medical/surgical intervention;
- the test result leads to discontinuation from the study, significant additional concomitant drug treatment, or other therapy;
- the test result is considered to be an AE by the investigator or sponsor.

Merely repeating an abnormal test, in the absence of any of the above conditions, does not constitute an AE. Any abnormal test result that is determined to be an error does not require reporting as an AE.

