The investigator must promptly report to the IRB/IEC or independent ethics committees (IEC) all changes in the research activity and all unanticipated problems involving risk to human subjects or others. This includes all SAEs that have occurred at the study site and all study-related SAEs that have resulted in an expedited safety report to the FDA (serious, unexpected SAEs possibly or probably related to study drug). The investigator must send all IRB/IEC documentation (including notifications and acknowledgements) to the sponsor or its designee. The investigator must not make any changes in the research without IRB/IEC approval, except where necessary to eliminate apparent immediate hazards to human subjects.

8.3.2 Reporting Requirements for Non-Serious Adverse Event

Non-serious systemic and skin AEs experienced after the randomization phase of the study will be reported on the AE eCRF pages, which will be submitted to the sponsor or its designee.

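### The SAP's rule for treatment-emergent adverse events omits the protocol's worsening criterion, and the SAP does not declare the change

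*SAP*

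**What the plan says.** Protocol 8.2.1 defines a treatment-emergent adverse event (TEAE) as "an event that emerges during treatment having been absent pre-treatment or worsens relative to the pre-treatment state". That is two alternative criteria: new after treatment, or worse after treatment.

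SAP 10.1, and SAP 7.3.1 in the same terms, use a single item instead: "Adverse events are categorized as either pre-treatment adverse events or treatmentemergent adverse events based on the response to the CRF question", the question being "Did the AE occur prior to patch administration". Neither SAP section mentions worsening or compares severity before and after the patch.

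Adverse event collection starts well before dosing. Protocol 6.2.11 states that "AEs are collected from the time of signing the informed consent form and throughout the study duration", and Protocol 8.2.1 adds that "This includes the time between screening and the first dosing". Protocol 6.1.3 sets the length of the wait: "Subjects will have up to 48 weeks to confirm and treat a qualifying cluster headache".

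SAP 12, which sets out departures from the protocol, covers the dropped Cochran-Mantel-Haenszel test and the dropped fixed-sequence procedure. It does not mention the TEAE definition.

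**The concern.** A reader of the report will take TEAE in the tables to mean what the protocol says. Under the SAP rule it means something narrower. An event already present when the patch goes on, which then gets worse, is the case the protocol's second criterion was written to catch, and the SAP has no step that catches it.

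The outputs that SAP 10.1 builds on this classification are those by severity, by relationship and by system organ class and preferred term. Comparing safety with placebo and assessing dose-response on tolerability are both secondary objectives (Protocol 2.2, SAP 2.1.2). If the drug aggravates existing complaints, that signal would be removed from the summaries meant to show it.

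**Working it through.** The documents give no figure to reproduce, and no formula applies. The check is to apply both rules to every kind of event, assuming that sites answer the CRF item correctly.

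| Event | Protocol 8.2.1 | SAP 7.3.1 and 10.1 |
|---|---|---|
| Starts after the patch | TEAE | CRF answer No: TEAE |
| Starts and resolves before the patch | Pre-treatment | CRF answer Yes: pre-treatment |
| Starts before, ongoing, does not worsen | Pre-treatment | CRF answer Yes: pre-treatment |
| Starts before, ongoing, worsens after; one record kept | TEAE | CRF answer Yes: pre-treatment |
| Starts before, ongoing, worsens after; worsening entered as a new record | TEAE | CRF answer No on the new record: TEAE |

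The two rules differ only in the fourth row.

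**Direction.** In that row the SAP removes an event that the protocol counts. No row goes the other way, so the SAP rule can only lower TEAE counts.

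**What decides between the last two rows.** Protocol 8.2.1 includes worsening of an existing medical condition in its definition of an adverse event, so a separate record is permitted. No section of either document requires one. The classification therefore depends on site practice.

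**Where the event would appear.** SAP 10.1 displays all adverse events in the listings and flags those that are treatment-emergent. A fourth-row event would be listed but not flagged, and it would be left out of the TEAE summaries.

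**Size.** The documents give no count of events ongoing at patch application, so the number affected cannot be derived. For scale only: at the planned 40 subjects per arm, one subject is 1/40 = 2.5%. SAP 12 says that fewer were randomized than planned, so one subject would weigh more than that, but the actual arm sizes are not given.

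**Data available to apply the protocol rule.** Protocol 8.3 already requires the date and time of onset for each event, and each event's severity is assessed. Onset relative to the first patch can be computed without the CRF item. A change in severity after the patch can be computed only if it was recorded.

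**The case against.** The strongest objection is that the CRF and its completion guidelines are not among the documents. The item asks whether the event occurred before the patch. Since the protocol treats worsening of an existing condition as an adverse event, a site could properly record a post-dose worsening as its own event, answer No, and so produce a TEAE. This stands, and it means that misclassification is possible but not certain. It does not rescue the SAP rule, because nothing in the plan makes sites do this.

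A reader might go further than the documents allow in four ways.

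- **That such events vanish from all safety reporting.** They do not. All adverse events are listed. Serious events, events leading to discontinuation and deaths each have a listing that is not worded as TEAE-only (SAP 10.1.1 to 10.1.3). SAP 10.1 promises a table or a listing for each topic, and the incidence summary by system organ class and preferred term depends on there being enough events.
- **That the long pre-dose window implies a large undercount.** Up to 336 days after randomization, against a final visit 1 to 8 days (+3) after dosing, shows that pre-dose onset is plausible. It does not measure the problem. Most pre-dose events are pre-treatment under both rules. Only an event still ongoing at the application, which worsens within days and is not re-entered, is affected. The 336 days is also a ceiling, not a typical wait.
- **That application-site reactions are undercounted.** These were the most common events in the earlier migraine trial (Protocol 1.2.1, Table 2). A reaction to the study patch cannot precede the patch, and any skin rating other than clear at the final visit must be recorded as an adverse event (Protocol 6.2.12, SAP 10.6).
- **That the pre-treatment record is unreliable throughout.** Protocol 8.3.2 says "Non-serious systemic and skin AEs experienced after the randomization phase of the study will be reported on the AE eCRF pages", and Table 4 shows no adverse event collection at screening, whereas Protocol 6.2.11 and 8.1 start at consent. This is a real but separate and minor inconsistency, confined to the period before randomization. Table 4 does collect events at Visit 2, and monthly calls assess them until dosing. It also partly works the other way: without an earlier record, a later worsening is more likely to be entered as new.

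It is also fair to object that the SAP is final and that SAP 12 already refers to the actual number randomized. A new instruction to sites may come too late for subjects already treated.

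**Conclusion.** The point holds. The SAP replaces the protocol's two-part TEAE definition with its first part only and does not declare the change. Relative to the protocol definition, the error runs one way, towards fewer TEAEs.

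The number of events affected cannot be derived and is probably small. The plan should be corrected, but this is not a threat to the trial's main conclusions. The verdict rests on two assumptions: that the CRF item is answered by the onset of the recorded event, and that at least some sites keep one record when an ongoing event worsens. If every site already opens a new record on worsening, the tables would match the protocol in practice, although the written rule would still not secure it.

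**What to change.** 1. In SAP 7.3.1 and 10.1, define a TEAE as an adverse event with onset at or after application of the first patch, or with earlier onset and increased severity at or after that time. Use the onset date and time collected under Protocol 8.3, and fall back on the CRF item when the onset time is missing.
2. Before database lock, and while still blinded, query every adverse event ongoing at patch application for post-dose worsening. Record any worsening as a separate event with its own onset time and severity.
3. If the change in severity cannot be recovered, state the narrower definition in SAP 12 and in the footnotes of the TEAE tables.

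The cost is a short SAP edit, a small programming change and a few queries. TEAE counts may rise slightly. Events that start after the patch are not affected.

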2.2 Secondary Objectives

- To compare the safety of C213 at doses of 1.9 mg and 3.8 mg (1.9 mg x 2 patches) to placebo in the acute treatment of cluster headache attacks
- To assess the dose-response relationship of C213 on efficacy and tolerability

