7.5 Safety Analysis

Safety analyses will be performed using the Safety population. Safety will be assessed by:

- Incidence of adverse events
- Physical exam including height and weight
- Vital signs including blood pressure
- Clinical laboratory determinations including serum chemistries and hematological parameters
- Pregnancy testing for women of child-bearing potential
- 12-lead ECGs
- Assessment of concomitant medications
- Investigator visual skin assessments

Adverse events will be coded using the latest version of MedDRA and will be summarized overall and by preferred term and system organ class. Adverse events will also be summarized by severity and relationship to study drug. Serious AEs and AEs leading to discontinuation of study drug will also be summarized.

All safety data will be listed by subject and parameter, separate listings of all abnormal laboratory findings and ECG findings will be provided, and clinically significant abnormalities will be recorded as AEs. Additional safety analyses will be described in the SAP.

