## 2.1.2 Secondary Objectives

The secondary objective is to compare the safety of C213 at doses of 1.9 mg and 3.8 mg (1.9 mg x 2 patches) to placebo and to assess the dose-response relationship of C213 on

Protocol: CP-2019-001 Page 8 of 26

Final Version 1.0

efficacy and tolerability.

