## 10.3 Vital Signs

All subjects will have vital signs (temperature, RR, BP, and HR) measured at the Screening, Randomization (Day 1), and End of Study (or early discontinuation) visits.

A by-subject listing of all vital sign data will be provided.

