## 10.6 Investigator Visual Skin Assessment

The Investigator will perform a visual skin assessment of bruising, erythema, and edema at the randomization visit (Visit 2) and at the End of Study (or early discontinuation) visit. Any adverse events including application site reactions will be documented on the appropriate eCRF page and must be followed until resolution or medically stable.

At the End of Study (or early discontinuation) visit, the entire surface area of the outer upper arm where the two patches were applied will be assessed for the following skin signs or symptoms. Any findings with an intensity rating of 1 (Mild intensity), 2 (Moderate intensity), or 3 (Severe intensity) must be recorded as an adverse event in the eCRF and followed to resolution.

Protocol: CP-2019-001 Page 23 of 26 Final Version 1.0

Bruising assessments (visual rating) will be performed using the following ratings:

Symptom	Intensity Rating (circle)
Bruising where	0 = Clear
C213 was applied?	1 = Mild intensity
T.F.	2 = Moderate intensity
	3 = Severe intensity

The following ratings will be used to describe the amount of erythema and edema indicative of irritation:

Symptom	Rating (circle)
Skin Erythema	0 = Clear
where C213 was applied?	1 = Mild intensity
Tr. F	2 = Moderate intensity
	3 = Severe intensity

Symptom	Rating (circle)
Skin Edema	0 = Clear
where C213 was applied?	1 = Mild intensity
	2 = Moderate intensity
	3 = Severe intensity

A by-subject data listing for bruising, erythema, and edema will be provided for each subject that has a rating of anything but 'Clear' at any visit and for those subjects who did not have the investigator skin assessment performed.

Protocol: CP-2019-001 Page 24 of 26

Final Version 1.0

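### SAP 10.1 and 10.6 could be met without any by-arm table of adverse events or skin reactions, although comparing safety with placebo is a stated objective

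*SAP*

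**What the plan says.** Both documents set a comparative safety objective. Protocol 2.2 has "To compare the safety of C213 at doses of 1.9 mg and 3.8 mg" against placebo, and SAP 2.1.2 has "The secondary objective is to compare the safety of C213". Each adds dose-response on tolerability.

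Protocol 7.5 says that adverse events "will be summarized overall and by preferred term and system organ class". It promises further summaries by severity and relationship, of serious events, and of events leading to discontinuation of study drug. None of this is conditional.

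The SAP is looser:

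- Section 10 says the safety analysis "will include summaries or data listings of the following safety and tolerability data".
- Section 10.1 says "An AE summary table or listing will be presented for the following", and the items are severity, relationship, discontinuation and SAEs. Sections 10.1.1 and 10.1.2 then specify listings for the last two.
- Section 10.1 also says that incidence summaries by SOC and preferred term "will be prepared if there are a sufficient number of adverse events".
- Section 10.6 says "A by-subject data listing for bruising, erythema, and edema will be provided for each subject", limited to subjects with a rating other than clear at any visit or with no skin assessment.
- Section 12 names two changes from the protocol: the CMH test and the fixed-sequence procedure are not used, because enrollment fell short. The AE summaries are not mentioned.

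**The concern.** A comparison between arms needs a count over a denominator in each arm. The SAP leaves the one table that would give this for adverse events to a judgement about the number of events. It does not say what number is enough, who decides, or whether the decision is made on pooled, blinded data.

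Application-site reactions are the tolerability effect that the sponsor's own earlier data lead one to expect, and they rose with dose. They would reach a by-arm table only through that conditional summary. If the table is judged unnecessary, a stated secondary objective ends with listings. The reader of the study report would have to count by hand, and would not know from the SAP that a protocol commitment had been relaxed.

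**Working it through.** The point rests on wording, and the plan has no figure of its own to reproduce. The check has three steps.

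**1. Output by output, protocol against SAP.**

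| Output | Protocol 7.5 | SAP |
|---|---|---|
| TEAEs by SOC and preferred term | Summary, unconditional | Summary only if events are judged sufficient (10.1) |
| AEs by severity, by relationship | Summary | Table or listing (10.1) |
| SAEs, AEs leading to discontinuation | Summary | Table or listing (10.1), then listing (10.1.1, 10.1.2) |
| Skin ratings | Named as a safety measure, no table promised | Listing of subjects not clear or not assessed (10.6) |

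A package made only of listings would satisfy every row of the SAP column. For the AE rows this departs from the protocol. For skin ratings it is a gap against the objective rather than a departure.

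**2. Does another route give the skin-reaction rate by arm?** SAP 10.6 and Protocol 6.2.12 require any rating of 1 to 3 to be recorded as an AE, so an AE incidence table would capture whether a reaction occurred. That is the conditional table. It would not reproduce the grades, because Protocol 6.2.12 has AE severity assessed by the functional definitions of 8.2.1.3, not by the 0 to 3 visual rating.

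**3. What would a table show in a small trial?** Inputs are from Protocol Table 2 (the earlier migraine study, the SOC for general disorders and administration-site conditions):

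- placebo 12/83 = 14.5%
- 1.9 mg 31/87 = 35.6%
- 3.8 mg 38/83 = 45.8%

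Expected subjects with an event = treated per arm × rate. The SAP plans 40 per arm, says fewer were randomized and gives no number, so the smaller sizes are assumptions.

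| Treated per arm | Placebo | 1.9 mg | 3.8 mg | Total |
|---|---|---|---|---|
| 10 | 1.4 | 3.6 | 4.6 | 9.6 |
| 15 | 2.2 | 5.3 | 6.9 | 14.4 |
| 20 | 2.9 | 7.1 | 9.2 | 19.2 |
| 40 | 5.8 | 14.3 | 18.3 | 38.3 |

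Two-sided Fisher power for 3.8 mg against placebo at these rates would be about 16%, 30%, 48% and 83%. The value of the table in a small trial is therefore descriptive. Nothing in the SAP says whether a total of 10, 14 or 19 would be enough to trigger it.

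**The case against.** The strongest reply is that the tables would probably be made. SAP 7.1 says tables are in general by treatment group, 7.1.2 and 7.1.3 refer to safety summaries, and 7.3.1 imputes missing AE severity and relationship, which suggests that tabulation was intended. With event counts like those above, a statistician would likely call them sufficient. With very few events, a listing is easy to count. All this is fair, but none of those sections names or guarantees a particular AE table.

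Three stronger readings are tempting, and the documents do not support them.

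- *The plan gives no safety output by arm, or loses the information.* Prior and concomitant medications (SAP 11.1) and exposure (11.2) are tabulated by arm without condition. All AEs are listed, with treatment-emergent ones flagged. For skin ratings, every subject who was not clear or not assessed is listed, so the rest of the Safety Population was clear. With treatment assignments and population counts, rates by arm can be rebuilt.
- *Laboratory values, vital signs and ECGs have the same fault.* For vital signs SAP 10.3 says "A by-subject listing of all vital sign data will be provided", and 10.2 and 10.5 are similar. But Protocol 7.5 itself planned listings of all safety data and of abnormal laboratory and ECG findings, and promised no by-arm or change-from-baseline tables. Such tables would add little: the post-dose values come 1 to 8 days after a single dose whose median Tmax was 20 minutes (1.9 mg) and 17.5 minutes (1.9 mg x 2) in Protocol Table 1. That SAP 7.1 defines change from baseline without using it is not an error.
- *The condition biases the comparison.* The trigger is the number of events, not a difference between arms, and no safety hypothesis test is specified, so no error rate is affected.

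**Conclusion.** The point holds for adverse events and skin reactions. The SAP replaces an unconditional protocol commitment with a conditional one, sets no threshold and does not declare the change. Its safety sections could be met in full without any by-arm table of AEs or skin ratings. The low enrollment cited in SAP 12 does not explain this, since counting subjects with an event by arm needs no minimum sample size.

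The consequence is a reporting gap against a stated objective, not lost data or a biased result. The sponsor should fix it, but it does not threaten the trial. The counts shown assume that the migraine study's rates carry over to cluster headache and that 10 to 40 subjects per arm were treated. The conclusion does not depend on either assumption.

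**What to change.** - **SAP 10.1:** delete the condition. Always produce by-arm n/N (%) tables of subjects with any TEAE, and of TEAEs by SOC and preferred term, by severity and by relationship. Listings can stay alongside. If the sponsor prefers a threshold, state it as a number fixed before unblinding and record it in Section 12 as a change from Protocol 7.5.
- **SAP 10.6:** tabulate bruising, erythema and edema ratings by arm, with the number assessed as denominator and a row for not done. That row matters because Visit 3 could be held by video.

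No change is needed to the listings of laboratory values, vital signs and ECGs. The cost is a few standard tables from data already collected, with no added subjects, visits or procedures.
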